6.1.2.5 PROGRESSION-FREE SURVIVAL

Progression-free survival is defined as the time from the date of randomization until the date of first documentation of definitive disease progression or date of death from any cause, whichever occurs first. Patients who die without a reported prior progression will be considered to have progressed on the day of their death. Patients who did not progress or are lost to follow-up will be censored at the day of their last tumor response assessment. If no baseline or post-baseline assessment is available, the patient will be censored at the date of randomization. If death or PD occurs after 2 or more consecutive missing tumor response assessments, censoring will occur at the date of the last response assessment prior to the missed assessments. The use of a new anticancer therapy prior to

the occurrence of PD will result in censoring at the date of last tumor response assessment prior to initiation of new therapy.

This variable will be analyzed using stratified log-rank test, and median PFS will be estimated via Kaplan-Meier methodology. PFS may not be formally analyzed at the time when the planned formal ORR analysis is conducted with approximately 120 patients who have had the opportunity to provide two efficacy assessments as it is expected that the majority of the patients from both treatment arms will not have progressed by the time of the primary ORR analysis (PFS may not be reliably estimated due to high censoring). Following the primary analysis of ORR, PFS may be analyzed at a later date. PFS will be analyzed using a stratified Cox regression model with treatment effect and stratification effect to estimate HR and 95% CI.

Censoring rules for PFS are summarized in Table 3.

TABLE 3: CENSORING RULES FOR PFS

Situation	Date of Progression or Censor	Censored/ Progressed
No baseline radiological tumor assessments	Randomization date	Censored
No post-baseline tumor assessments and no death reported before data cut-off	Randomization date	Censored
Disease progression	Date of progression	Progressed
No disease progression	Date of last tumor assessment	Censored
Treatment discontinuation for toxicity or other reasons with no disease progression per IRC	Date of last tumor assessment	Censored
Patient lost to follow-up without disease progression	Date of last tumor assessment	Censored
Death before first tumor assessment	Date of death	Progressed
Death between adequate tumor assessments	Date of death	Progressed

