Death or disease progression after ≥ 2 missed tumor assessments	Date of last tumor assessment before missed assessments or randomization date if no other tumor assessment in between	Censored
Withdrawal due to symptomatic deterioration without further tumor assessments	Date of last tumor assessment before discontinuation	Censored
Patient use of any anti-cancer therapy and/or surgery for curative intent.	Date of last tumor assessment prior to therapy or surgery, whichever occurs first	Censored
Note: Progression-free survival = date of even	t / censor – randomization date + 1	

Once the progression and survival dates are derived, PFS will be calculated as follows for patients with a PFS event:

PFS (days) = date of PD or death due to any case – randomization date + 1

(with censoring indicator = event)

For those patients who are censored for a PFS event:

[figure not shown]
PFS (days) = date of censoring – randomization date + 1

(with censoring indicator = censored)

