6.2 ANALYSIS METHODS: DOR AND PFS

The date of definitive progression will be the timepoint at which progression is first identified and confirmed by the independent radiographic committee. Death following the discontinuation of study drug will be considered as an event for the DOR and PFS calculation. Data will be censored on the date of the last tumor assessment (including assessments with a Not Evaluable (NE) outcome) for patients who:

- Start alternative anti-tumor therapy prior to disease progression
- Do not have disease progression within 30 days after discontinuation of study drug(s)

TG Therapeutics, Inc. UTX-IB-301 SAP

secondary outcomes will be tested:

If the primary efficacy analysis of ORR is statistically significant for the ITT population, the following

- Complete response rate
- Duration of response
- · Time to response

For each of these outcomes, ublituximab + ibrutinib will be compared to ibrutinib. The Hochberg approach will be used to control the type I error rate. The null hypotheses state that the secondary outcomes do not differ between ublituximab + ibrutinib and ibrutinib. The three p-values associated with these three secondary outcomes are denoted p_1 , p_2 , and p_3 . The ordered p-values, from largest to smallest, are denoted $p_{(1)} \ge p_{(2)} \ge p_{(3)}$. Specifically:

- If $p_{(1)}$ is less than 0.05, all three null hypotheses will be rejected.
- Otherwise, if $p_{(2)}$ is less than 0.025, the null hypotheses associated with $p_{(2)}$ and $p_{(3)}$ will be rejected.
- Otherwise, if $p_{(3)}$ is less than 0.0167, the null hypothesis associated with $p_{(3)}$ will be rejected.

If the primary efficacy analysis of ORR is not statistically significant, the secondary efficacy variable defined above will not be formally conducted.

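### SAP Table 3, read literally, censors some deaths after withdrawal for symptomatic deterioration that the PFS definition and SAP 6.2 count as events

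*SAP*

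**What the plan says.** **SAP 6.1.2.5, text.** PFS runs from randomization to the "first documentation of definitive disease progression or date of death from any cause, whichever occurs first". It adds: "Patients who die without a reported prior progression will be considered to have progressed on the day of their death". Two exceptions follow. The first is "If death or PD occurs after 2 or more consecutive missing tumor response assessments, censoring will occur" at the last assessment before the gap. The second is that new anticancer therapy before progression censors at the assessment preceding it.

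**SAP 6.1.2.5, Table 3.** The row "Withdrawal due to symptomatic deterioration without further tumor assessments" is given the date "Date of last tumor assessment before discontinuation" and the status censored. Deaths are events in two rows: death before the first assessment, and "Death between adequate tumor assessments". One censoring row, for patients with no post-baseline assessment, does require that no death was reported by data cut-off.

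**SAP 6.2.** "Death following the discontinuation of study drug will be considered as an event for the DOR and PFS calculation". The same paragraph then censors, at the last assessment, patients who start other anti-tumor therapy before progression and patients with no progression within 30 days of stopping study drug.

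**Protocol 11.10.2.1.6.** The definition and the text rules match the SAP text. There is no rule for symptomatic deterioration; Table 3 adds it.

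**The concern.** A patient who declines, becomes too ill to be scanned and then dies matches the deterioration row closely, and that row ends in censoring. The PFS text and SAP 6.2 make the same death an event. Two programmers working from the same SAP could therefore code this patient differently, and the choice might be settled only after the data have been seen.

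The patients concerned are not a random subset. They leave because they are getting worse, so censoring them is likely to be informative, and the Kaplan-Meier curve would tend to sit too high. Death may also be their only PFS event: Protocol 10.8 does not accept worsening constitutional symptoms as definitive progression without objective evidence. (Protocol 4.1 lists worsening disease-related symptoms among the forms progression can take, so the protocol is not fully aligned here; 10.8 is the operational definition.)

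**Working it through.** The documents give no PFS event count, target hazard ratio or deterioration rate to reproduce, so the check is mainly of text.

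**Step 1: one patient, each rule in turn.** Take a patient with baseline and at least one post-baseline scan, withdrawal for deterioration, no later scan, and death before two assessments are missed.

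- Deterioration row of Table 3: fits; censored at the last scan.
- Row for death before the first assessment: does not fit, because there was an assessment.
- Row for death between assessments: does not fit literally, because no later assessment exists.
- Row for death after two or more missed assessments: does not fit yet.
- PFS text: event on the day of death.
- SAP 6.2, sentence on death after discontinuation: event.
- SAP 6.2, 30-day rule: censored, if the death is not itself treated as progression.

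No statement ranks these rules.

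**Step 2: the sibling rows.** The rows for no progression, treatment discontinuation and loss to follow-up also lack a death condition. Each is at least worded for patients without progression, and the text deems a patient who dies to have progressed, so they can be read as not applying to deaths. The discontinuation row ties this to progression per IRC, which weakens that reading. The deterioration row has no progression condition at all, so it is the clearest case.

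**Step 3: how long the conflict lasts.** After a second missed assessment, the text itself censors the death, so the conflict ends there. With 28-day cycles and scans after cycles 2, 4 and 6 and then every 3 cycles (SAP 3.1 and 3.2), scans fall at weeks 8, 16, 24, 36, 48 and so on.

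- Last scan week 8: second missed scan week 24; 24 − 8 = 16 weeks.
- Last scan week 16: second missed scan week 36; 36 − 16 = 20 weeks.
- Last scan week 24: second missed scan week 48; 48 − 24 = 24 weeks. Later scans also give 24 weeks.
- Follow-up schedule, about every 3 months: 2 × 3 = about 6 months.

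Scans on the treatment schedule have a window of ±7 days.

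**Step 4: can a size be given?** Only on assumptions. Let f be the share of an arm's true PFS events recoded as censored, with constant hazards and ignoring the time between last scan and death. The median is then multiplied by 1/(1 − f):

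- f = 10%: 1/0.90 = 1.11.
- f = 20%: 1/0.80 = 1.25.

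The apparent hazard ratio (A versus B) is about HR × (1 − fA)/(1 − fB). For an assumed true HR of 0.60:

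- fA = 10%, fB = 20%: 0.60 × 0.90/0.80 = 0.675.
- fA = 20%, fB = 10%: 0.60 × 0.80/0.90 = 0.533.
- fA = fB: 0.60, unchanged.

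The documents support no value of f in either arm.

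**The case against.** The best defence is that the SAP already answers the question. Table 3 is presented as a summary of the rules. The text counts any death without prior progression, the formula under the table takes progression or death as the event, and SAP 6.2 says death after discontinuation counts. A separate censoring row for deaths after two or more missed assessments makes sense only if earlier deaths are events. Read strictly, the no-progression row would also censor every death without progression and contradict the table's own death rows, so the coherent reading is that these rows describe patients who have had no event.

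This is persuasive about intent. A reader might infer that the sponsor means to drop these deaths from PFS; the documents do not support that. What remains is that the reader must work out the precedence, and that Table 3 states the death condition in one censoring row and omits it in another where death is the likely next event.

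Availability of death dates is a fair limit. Protocol 6.1 and SAP 3.1 plan follow-up for progression and/or survival about every 3 months, but Protocol 6.4, 8.6 and 10 mention progression only. The SAP does not say whether withdrawal means from treatment or from the study, so some later deaths may be unknown.

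**Conclusion.** The conflict is real but narrow. It concerns deaths from any cause, not only CLL deaths, after at least one post-baseline scan and before a second missed assessment: 16 to 24 weeks after the last scan on the treatment schedule, about 6 months on the follow-up schedule. Within that window a literal reading of Table 3 would tend to overstate PFS, assuming that withdrawal for deterioration predicts death.

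A reader might also infer that the hazard ratio is pulled towards 1 because the worse arm has more such deaths. That does not follow. The bias depends on the share of events recoded in each arm, not on the number of deaths, and the illustration moves 0.60 to 0.675 or to 0.533 according to which arm is given the larger share. Neither size nor direction can be taken from the documents.

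The consequence is limited. PFS is secondary, has no formal test in Protocol 11.10.2.1.6, is outside the SAP's Hochberg list, and may not be formally analysed at the time of the ORR analysis. It is nonetheless given a stratified log-rank test and a Cox hazard ratio in the SAP, so the event rule should be unambiguous. ORR is unaffected. Table 3 is titled for PFS only; DOR, which is in the Hochberg list, is touched through the internal conflict in SAP 6.2.

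**What to change.** Make three changes to the SAP.

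1. Add one precedence statement to Table 3 and SAP 6.2: a reported death without prior progression is a PFS event on the date of death, and this overrides the rows for no progression, treatment discontinuation, loss to follow-up and symptomatic deterioration, except where the existing rules for two or more missed assessments or for new anticancer therapy apply.
2. Reword the row "Death between adequate tumor assessments" so that it also covers deaths after the last assessment with fewer than two missed assessments.
3. Reconcile the 30-day censoring rule in SAP 6.2 with that section's statement that death after discontinuation is an event, for both PFS and DOR.

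A general statement is better than editing the deterioration row alone, because the other rows share the omission. The cost is a few lines of SAP text and derivation code. It uses deaths known from the planned follow-up and needs no new data; some deaths after withdrawal from the study may still go unrecorded.

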4.1 EFFICACY ENDPOINTS

Progression-free survival (PFS)

PFS is defined as the interval from randomization to the earlier of the first documentation of definitive disease progression or death from any cause.

Definitive disease progression based on standard criteria (Hallek et al. 2008) and occurring for any reason (i.e., increasing lymphadenopathy, organomegaly or bone marrow involvement; decreasing platelet count, hemoglobin, or neutrophil count; or worsening of disease-related symptoms) other than lymphocytosis.

Overall response rate (ORR)

ORR is defined as sum of CR and PR rates.

Duration of Response (DOR)

Defined as the interval from the first documentation of CR or PR to the earlier of the first documentation of disease progression or death from any cause.

Complete Response (CR) Rate

CR rate is defined as the proportion of patients who achieve a CR.

Minimal Residual Disease (MRD) Negativity Rate

MRD negativity rate is defined as the proportion of patients who are MRD negative, excluding any patients who remain on study treatment at the time of the analysis and have a Cycle 1/Day 1 start date less than 6 months from the time of the analyses. For the sake of clarity, the MRD negative analysis will exclude those patients that are too early to evaluate because MRD negativity is only tested for patients on study \geq 6 months. Patients who drop off study for any reason prior to their 6-month visit will be included in the analysis.

UTX-IB-301

 $\frac{\textbf{Time to Response (TTR)}}{\textbf{TTR is defined as the interval from randomization to the first documentation of CR or PR}$

UTX-IB-301 Dated: 31 July 2017 (Ver. 2.5) Patients must meet all of the following inclusion criteria and none of the exclusion criteria to be eligible for participation in this study.

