Atrial fibrillation and atrial flutter (range, 6 to 9%) have occurred in patients treated with ibrutinib, particularly in patients with cardiac risk factors, hypertension, acute infections, and a previous history of atrial fibrillation. Periodically monitor patients clinically for atrial fibrillation. Patients who develop arrhythmic symptoms (e.g., palpitations, lightheadedness) or new onset dyspnea should have an ECG performed. If atrial fibrillation persists, consider the risks and benefits of ibrutinib treatment and dose modification in the prescribing information.

Hypertension

Hypertension (range, 6 to 17%) has occurred in patients treated with ibrutinib with a median time to onset of 4.6 months (range, 0.03 to 22 months). Monitor patients for new onset hypertension or hypertension that is not adequately controlled after starting ibrutinib. Adjust existing antihypertensive medications and/or initiate anti-hypertensive treatment as appropriate.

Second Primary Malignancies

Other malignancies (range, 3 to 16%) including non-skin carcinomas (range, 1 to 4%) have occurred in patients treated with ibrutinib. The most frequent second primary malignancy was non-melanoma skin cancer (range, 2 to 13%).

Tumor Lysis Syndrome

UTX-IB-301

Tumor lysis syndrome has been infrequently reported with ibrutinib therapy. Assess the baseline risk (e.g., high tumor burden) and take appropriate precautions. Monitor patients closely and treat as appropriate.

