11.10.2.1.6 PROGRESSION-FREE SURVIVAL

Progression-free survival is defined as the time from the date of randomization until the date of first documentation of definitive disease progression or date of death from any cause, whichever occurs first. Patients who die without a reported prior progression will be considered to have progressed on the day of their death. Patients who did not progress or are lost to follow-up will be censored at the day of their last tumor response assessment. If no baseline or post-baseline assessment is available, the patient will be censored at the date of randomization. If death or PD occurs after 2 or more consecutive missing tumor response assessments, censoring will occur at the date of the last response assessment prior to the missed assessments. The use of a new anticancer therapy prior to the occurrence of PD will result in censoring at the date of last tumor response assessment prior to initiation of new therapy.

This variable will be analyzed via Kaplan-Meier methodology. The median PFS will be estimated for each arm, however no formal hypothesis testing will be conducted.

UTX-IB-301

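### The PFS censoring rule in SAP Table 3, 6.1.2.5 and 6.2 is not limited to CLL therapy, so local treatment of a second cancer can censor PFS, and the sections disagree on the censoring date

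*SAP*

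**What the plan says.** Protocol 4.1 sets the endpoint: "PFS is defined as the interval from randomization to the earlier of the first documentation of definitive disease progression or death from any cause". SAP 6.2 adds: "Death following the discontinuation of study drug will be considered as an event for the DOR and PFS calculation".

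The rule on subsequent therapy appears in three forms.

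- **Running text.** Protocol 11.10.2.1.6 states: "The use of a new anticancer therapy prior to the occurrence of PD will result in censoring", dated to the last response assessment before the new therapy. SAP 6.1.2.5 repeats this.
- **SAP Table 3**, introduced as a summary of the PFS censoring rules, has the row "Patient use of any anti-cancer therapy and/or surgery for curative intent". The date is "Date of last tumor assessment prior to therapy or surgery, whichever occurs first" and the status is censored.
- **SAP 6.2**, which covers both DOR and PFS, censors patients who "Start alternative anti-tumor therapy prior to disease progression". The date is that of the last tumour assessment, including non-evaluable ones. It is not tied to the start of the therapy.

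Protocol 9.2.1.1 reports other malignancies in 3 to 16% of ibrutinib-treated patients, non-skin carcinomas in 1 to 4% and non-melanoma skin cancer in 2 to 13%. Both arms receive ibrutinib. A second malignancy is reported on the SAE form (Protocol 12.9.6) and is not by name a reason to stop treatment (Protocol 6.4). Protocol 8.2.2 describes ibrutinib as held around surgery.

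**The concern.** Censoring at subsequent therapy is normally meant for patients whose CLL course is altered by a new CLL treatment. Here the trigger is any cancer treatment, and Table 3 names curative surgery. A patient with a second primary may have it removed, continue or resume study drug, and attend every CLL scan. Under the literal rule none of that later follow-up counts.

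Two kinds of event are lost: observed CLL progressions, and deaths after the second cancer was treated. The second conflicts with an endpoint that counts every death. The differing dates mean that two programmers following the SAP could derive different PFS times for the same patient. DOR is exposed too. SAP 6.1.2.2 gives it no censoring rule of its own, so the 6.2 wording governs an outcome in the Hochberg family.

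**Working it through.** **The provisions side by side**

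| Place | Trigger | Limited to CLL? | Before progression? | Censoring date |
|---|---|---|---|---|
| Protocol 11.10.2.1.6; SAP 6.1.2.5 text | New anticancer therapy | No | Yes | Last assessment before the therapy |
| SAP Table 3 | Any anti-cancer therapy and/or curative surgery | No | Not in the row | Last assessment before therapy or surgery |
| SAP 6.2 (DOR and PFS) | Alternative anti-tumour therapy | No | Yes | Last tumour assessment |

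**A worked patient.** A skin cancer is excised between the cycle 6 and cycle 9 assessments. CLL scans continue, and the IRC finds progression after cycle 15.

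- Table 3: censored at the cycle 6 assessment.
- 6.2, if excision counts as alternative therapy: censored at the last tumour assessment, which can be a scan after the excision.
- 6.2, if excision does not count: a PFS event at the cycle 15 assessment.

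**How many patients could be involved.** The inputs are about 120 patients (SAP 3.6) and the ranges in Protocol 9.2.1.1.

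- All second malignancies: 120 × 0.03 = 3.6 to 120 × 0.16 = 19.2.
- Non-melanoma skin cancer: 120 × 0.02 = 2.4 to 120 × 0.13 = 15.6.
- Non-skin carcinoma: 120 × 0.01 = 1.2 to 120 × 0.04 = 4.8.
- Chance of at least one second malignancy at the 3% end: 1 − 0.97^120 = 0.974.

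The share treated while progression-free and on study drug is not given. Assumed shares of 25%, 50% and 100% of all second malignancies give 0.9–4.8, 1.8–9.6 and 3.6–19.2 patients.

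**How many PFS events are lost.** The readable text gives no PFS event target or hazard, so there is no planned figure to reproduce. Assumptions:

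- N = 120, with 3 years of follow-up;
- constant PFS hazard λ of 0.10 or 0.20 per year;
- 3-year second-cancer risk r of 2% to 16%, so μ = −ln(1 − r)/3 per year;
- second cancers independent of CLL progression, and every one treated and caught by the rule.

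Formulas:

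- Events without the rule: N(1 − e^(−3λ)).
- Events with the rule: N · λ/(λ+μ) · (1 − e^(−3(λ+μ))).
- Patients censored by the rule: N · μ/(λ+μ) · (1 − e^(−3(λ+μ))).

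| r | λ | μ | Patients censored | Events without rule | Events with rule | Lost |
|---|---|---|---|---|---|---|
| 2% | 0.10 | 0.0067 | 2.1 | 31.1 | 30.8 | 0.3 (1.0%) |
| 2% | 0.20 | 0.0067 | 1.8 | 54.1 | 53.7 | 0.5 (0.9%) |
| 16% | 0.10 | 0.0581 | 16.7 | 31.1 | 28.7 | 2.4 (7.8%) |
| 16% | 0.20 | 0.0581 | 14.6 | 54.1 | 50.1 | 4.0 (7.4%) |

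In the worst case the confidence interval for the log hazard ratio widens by a factor of √(31.1/28.7) = 1.04. Deaths caused by the second cancer are not in this model and would add to the loss.

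**The case against.** Several stronger readings are tempting, and the documents do not support them.

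- **That the row also censors treatment given after progression.** The row alone lacks the qualifier. But Table 3 summarises text that states it, and 6.2 repeats it, so the fair reading is therapy before progression.
- **That the affected patient is always still on study drug.** This is possible, not certain. Protocol 6.4 lists interventions the protocol does not permit, and investigator discretion. Protocol 8.6 lists intercurrent illness that prevents further treatment. Some patients would stop.
- **That Table 3 alone creates the breadth by naming surgery.** Protocol 5.2 already counts surgery and radiotherapy as cancer therapy. The breadth is in all three statements.
- **That harm by arm would be hidden.** Second malignancies are reported as SAEs, and treatment-emergent events are tabulated by drug received (SAP section 8). The documents give no second-cancer rate by arm, and nothing shows that adding ublituximab changes the risk.
- **That PFS and DOR are shown to be handled differently.** Section 6.2 has one trigger for both. They diverge only if its wording is read more narrowly than Table 3.

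The size is also small. If second cancers are independent of CLL progression, the censoring is non-informative for progression and costs information without biasing the comparison. The protocol plans no formal PFS test, the SAP's log-rank test is outside the Hochberg family, and ORR is untouched. Whether to censor at systemic therapy for another cancer is a legitimate choice of estimand.

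What remains is that no text limits the trigger to CLL, the literal result conflicts with counting deaths from any cause, and the date rules differ. The sponsor may have meant CLL therapy, but neither document says so.

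**Conclusion.** The point holds as a defect of rule wording with a modest effect. Followed literally, local curative treatment of a second primary censors PFS at the preceding scan and discards later CLL progression or death. The choice between the Table 3 and 6.2 dates is also left open.

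Under the stated assumptions about 2 to 17 of 120 patients would be censored this way, and about 1 to 8% of PFS events lost, at most about 4 across both arms. These figures rest on an assumed 3-year horizon (the protocol gives no time frame for its percentages), assumed hazards, independence, and every second cancer being treated and captured. A smaller share captured lowers them; deaths from the second cancer raise the loss. No bias between arms is shown. The ORR analysis is unaffected. The main reason to settle it is that PFS will be reported with a hazard ratio and that DOR, a tested secondary outcome, uses the same 6.2 trigger.

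**What to change.** Use one trigger and one date in the 6.1.2.5 text, Table 3 and 6.2, for PFS and DOR alike. Suggested wording: *New anti-CLL therapy (systemic therapy, radiotherapy or surgery directed at CLL) started before IRC-confirmed progression: censored at the last tumour assessment before that therapy.*

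Add that local or surgical treatment of a second primary malignancy does not censor PFS or DOR. Flag the indication (CLL or other) on post-baseline anticancer therapy. For systemic chemotherapy given for a non-CLL cancer, run a sensitivity analysis with such patients censored and not censored.

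The cost is SAP wording, one data flag and a little programming, all of which should be settled before database lock, when SAP section 2 requires the plan to be final. The drawback is that some non-CLL treatment with possible activity against CLL stays in follow-up; the sensitivity analysis shows whether systemic treatment of that kind matters.
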